8.5 Diet/Activity/Other Considerations

8.5.1 Diet

Subjects should maintain a normal diet unless modifications are required to manage an AE such as diarrhea, nausea or vomiting.

8.5.2 Contraception

Pembrolizumab may have adverse effects on a fetus in utero. Furthermore, it is not known if pembrolizumab has transient adverse effects on the composition of sperm. Non-pregnant, non-breast-feeding women may be enrolled if they are willing to use 2 methods of birth

control or are considered highly unlikely to conceive. Highly unlikely to conceive is defined as 1) surgically sterilized, or 2) postmenopausal (a woman who is ≥ 45 years of age and has not had menses for greater than 1 year will be considered postmenopausal), or 3) not heterosexually active for the duration of the study. The two birth control methods can be either two barrier methods or a barrier method plus a hormonal method to prevent pregnancy. Subjects should start using birth control from study Visit 1 throughout the study period up to 120 days after the last dose of study therapy.

The following are considered adequate barrier methods of contraception: diaphragm, condom (by the partner), copper intrauterine device, sponge, or spermicide. Appropriate hormonal contraceptives will include any registered and marketed contraceptive agent that contains an estrogen and/or a progestational agent (including oral, subcutaneous, intrauterine, or intramuscular agents).

Subjects should be informed that taking the study medication may involve unknown risks to the fetus (unborn baby) if pregnancy were to occur during the study. In order to participate in the study they must adhere to the contraception requirement (described above) for the duration of the study and during the follow-up period defined in section 7.2.2-Reporting of Pregnancy and Lactation to the Merck. If there is any question that a subject will not reliably comply with the requirements for contraception, that subject should not be entered into the study.

8.5.3 Use in Pregnancy

If a subject inadvertently becomes pregnant while on treatment with pembrolizumab, the subject will immediately be removed from the study. The site will contact the subject at least monthly and document the subject's status until the pregnancy has been completed or terminated. The outcome of the pregnancy will be reported to the Merck without delay and within 24 hours to the Merck and within 2 working days to Merck if the outcome is a serious adverse experience (e.g., death, abortion, congenital anomaly, or other disabling or life-threatening complication to the mother or newborn).

The study investigator will make every effort to obtain permission to follow the outcome of the pregnancy and report the condition of the fetus or newborn to the Merck. If a male subject impregnates his female partner the study personnel at the site must be informed immediately and the pregnancy reported to Merck and followed as described above and in Section 7.2.2.

8.5.4 Use in Nursing Women

It is unknown whether pembrolizumab is excreted in human milk. Since many drugs are excreted in human milk, and because of the potential for serious adverse reactions in the nursing infant, subjects who are breast-feeding are not eligible for enrollment.

8.6 Subject Withdrawal/Discontinuation Criteria

Subjects may withdraw consent at any time for any reason or be dropped from the trial at the discretion of the investigator should any untoward effect occur. In addition, a subject may be withdrawn by the investigator if enrollment into the trial is inappropriate, the trial plan is violated, or for administrative and/or other safety reasons. Specific details regarding discontinuation or withdrawal are provided in Section 7.1.4 – Other Procedures.

A subject must be discontinued from the trial for any of the following reasons:

- The subject or legal representative (such as a parent or legal guardian) withdraws consent.
- Confirmed radiographic disease progression

Note: For unconfirmed radiographic disease progression, please see Section 5.2.2

Note: A subject may be granted an exception to continue on treatment with confirmed radiographic progression if clinically stable or clinically improved, please see Section 7.1.2.7.1

- Unacceptable adverse experiences as described in Section 5.2.1.2
- Intercurrent illness that prevents further administration of treatment
- Investigator's decision to withdraw the subject
- The subject has a confirmed positive serum pregnancy test
- Noncompliance with trial treatment or procedure requirements
- The subject is lost to follow-up
- Completed 24 months of uninterrupted treatment with pembrolizumab or 35 administrations of study medication, whichever is later.

Note: 24 months of study medication is calculated from the date of first dose. Subjects who stop pembrolizumab after 24 months may be eligible for up to one year of additional study treatment if they progress after stopping study treatment provided they meet the requirements detailed in Section 7.1.5.5

- Administrative reasons

The End of Treatment and Follow-up visit procedures are listed in Section 6 (Protocol Flow Chart) and Section 7.1.5 (Visit Requirements). After the end of treatment, each subject will be followed for 30 days for adverse event monitoring (serious adverse events will be collected for 90 days after the end of treatment as described in Section 7.2.3.1). Subjects

who discontinue for reasons other than progressive disease will have post-treatment follow-up for disease status until disease progression, initiating a non-study cancer treatment, withdrawing consent or becoming lost to follow-up. After documented disease progression each subject will be followed by telephone for overall survival until death, withdrawal of consent, or the end of the study, whichever occurs first.

8.6.1 Discontinuation of Study Therapy after CR

Discontinuation of treatment may be considered for subjects who have attained a confirmed CR that have been treated for at least 24 weeks with pembrolizumab and had at least two treatments with pembrolizumab beyond the date when the initial CR was declared. Subjects who then experience radiographic disease progression may be eligible for up to one year of additional treatment with pembrolizumab via the Second Course Phase at the discretion of the investigator if no cancer treatment was administered since the last dose of pembrolizumab, the subject meets the safety parameters listed in the Inclusion/Exclusion criteria, and the trial is open. Subjects will resume therapy at the same dose and schedule at the time of initial discontinuation. Additional details are provided in Section 7.1.5.5.

8.7 Subject Replacement Strategy

A subject who discontinues from the trial will not be replaced.

8.8 Clinical Criteria for Early Trial Termination

Early trial termination will be the result of the criteria specified below:

1. Quality or quantity of data recording is inaccurate or incomplete
2. Poor adherence to protocol and regulatory requirements
3. Incidence or severity of adverse drug reaction in this or other studies indicates a potential health hazard to subjects
4. Plans to modify or discontinue the development of the study drug

In the event of Merck decision to no longer supply study drug, ample notification will be provided so that appropriate adjustments to subject treatment can be made.

9.0 TRIAL FLOW CHART

9.1 Study Flow Chart

Trial Period:	Screening Phase	Treatment Cycles ^a						End of Treatment	Post-Treatment		
		1	2	3	4	To be repeated beyond 6 cycles		Discon	Safety Follow-up	Follow Up Visits ^b	Survival Follow Up ^c
						5	6				
Scheduling Window (Days) ^d :	-28 to -1		± 3	± 3	± 3	± 3	± 3	± 3	± 7	± 7	± 7
Administrative Procedures											
Informed Consent ^e	X										
Inclusion/Exclusion Criteria	X										
Demographics and Medical History	X										
Prior and Concomitant Medication Review ^f	X	X	X	X	X	X	X	X	X		
Clinical Procedures/Assessments											
Review Adverse Events ^g	X	X	X	X	X	X	X	X	X	X	
12-Lead ECG	X										
Physical Examination	X	X	X	X	X	X	X	X			
Height, Weight, and Vital Signs (T, P, RR, BP) ^h	X	X	X	X	X	X	X	X			
ECOG Performance Status	X	X	X	X	X	X	X	X			
Post-study Anticancer Therapy Status									X	X	
Survival Status											X
Trial Treatment Administration											
Pembrolizumab ⁱ		X	X	X	X	X	X				
Laboratory Procedures/Assessments:											
Pregnancy Test – Urine or Serum β-HCG ^j	X										
PT/INR and aPTT ^k	X										
CBC with Differential ^l	X		X	X	X	X	X ^l	X	X ^l		

Trial Period:	Screening Phase	Treatment Cycles ^a						End of Treatment	Post-Treatment		
		1	2	3	4	To be repeated beyond 6 cycles			Safety Follow-up	Follow Up Visits ^b	Survival Follow Up ^c
Treatment Cycle/Title:	Screening (Visit 1)					5	6				
								At time of discon	30 days post discon	Every 6 weeks post discon	Every 12 weeks
Scheduling Window (Days) ^d :	-28 to -1	± 3	± 3	± 3	± 3	± 3	± 3	± 3	± 7	± 7	± 7
Chemistry Panel ¹	X		X	X	X	X	X ¹	X	X ¹		
Urinalysis ¹	X										
T3, FT4 and TSH ¹	X		X		X		X		X		
Serum carcinoembryonic antigen (CEA) ¹	X		X		X		X ¹				
Serum CA 19-9 ¹	X		X		X		X ¹				
Blood for Genetics ^m		X									
Correlative Blood Samples (DNA) ⁿ		X	X	X				X			
Correlative Blood Samples (RNA) ⁿ		X	X	X				X			
Correlative Blood Samples (plasma) ⁿ		X									
Correlative Blood Samples (serum) ⁿ		X									
Efficacy Measurements											
Tumor Imaging ^o	X		X		X		X	X ^p		X	
Tumor Tissue Collection											
Archival and/or Newly-Obtained Tissue Collection	X	-----X----- ^q						X			

- a. Unless otherwise specified, assessments/procedures are to be performed on Day 1 and prior to the first dose of treatment for each cycle.
- b. In subjects who discontinued study therapy without documented disease progression, every effort should be made to continue monitoring their disease status by radiologic imaging every 6 weeks (\pm 7 days) if prior to 1 year or every 9 weeks (\pm 7 days) if after 1 year, until (1) the start of new anti-cancer treatment, (2) disease progression as assessed by imaging , (3) death, or (4) the end of the study, whichever occurs first.
- c. After the start of new anti-cancer treatment or documented disease progression by the imaging , the subject should be contacted by telephone every 12 weeks to assess for survival status. Note: All efforts should be made to ensure telephone contact occurs at least 90 days post discontinue to capture SAEs
- d. Unless otherwise specified, the window for each visit is \pm 3 days. Cycle 1 treatment must be given within 3 days of enrollment.
- e. Written consent must be obtained prior to performing any protocol specified procedure. Results of a test performed prior to the subject signing consent as part of routine clinical management are acceptable in lieu of a screening test if performed within the specified time frame (e.g., within 28 days prior to the first dose of trial treatment).
- f. Prior medications – Record all medications taken within 28 days of screening visit. Concomitant medications – Enter new medications started during the trial through the Safety Follow-up visit. Record all medications taken for SAEs
- g. Record all AEs occurring within 30 days after the last dose of trial treatment. Report all SAEs (related and unrelated to trial treatment) and ECIs occurring up until 90 days after the last dose of trial treatment or the start of new anti-cancer treatment, whichever comes first. Afterwards, report only SAEs and ECIs that are related to trial treatment.
- h. Height will be measured at Visit 1 only. Vitals Signs include temperature, pulse, respiratory rate, and blood pressure.
- i. Pembrolizumab should be administered on Day 1 of each three week cycle after all procedures/assessments have been completed.
- j. For women of reproductive potential, a serum pregnancy test should be performed within 72 hours prior to first dose of trial treatment. A urine test can be considered if serum is not appropriate. Pregnancy tests (serum and/or urine tests) should be repeated if required by local guidelines.
- k. Coagulation factors (PT/INR and aPTT) should be tested as part of the screening procedures for all subjects.
- l. Laboratory tests for screening are to be performed within 10 days prior to the first dose of trial treatment.
After Cycle1, lab samples can be collected up to 72 hours prior to the scheduled time point. To be repeated every 2 cycles after Cycle 6. Unresolved abnormal labs that are drug relatedAEs should be followed until resolution. Labs do not need to be repeated after the end of treatment if labs are within normal range. Serum CEA and CA 19-9 should be collected at screening (baseline) and every 6 weeks (conducted at corresponding study visits) through Week 24 (6 months). After Week 24, serum CEA and CA19-9 should be collected every 12 weeks until study treatment discontinuation..
- m. This sample should be drawn for planned genetic analysis of DNA and drug response unless there is either a documented law or regulation prohibiting collection, or unless the IRB/IEC does not approve of the collection of the sample for these purposes.
- n. Whole blood sample for correlative studies should be collected at Cycle 1, Day 1- Pre-dose, Cycle 2 Day 1- Pre-dose, Cycle 3 Day 1 Pre-dose and again at treatment discontinuation. Blood for serum and blood for plasma to be collected only prior to Cycle 1 Day 1.
- o. Baseline tumor imaging will be performed within 14 days prior to enrollment. Scans performed as part of routine clinical management are acceptable for use as the baseline scan if they are of diagnostic quality . The exact same image acquisition and processing parameters should be used throughout the study. The first on-study imaging time point will be performed 6 weeks (\pm 7 days) or earlier if clinically indicated and will continue to be performed every 6 weeks (\pm 7 days) regardless of any treatment delays. Following week 24 (6 months), imaging time point will occur every 12 weeks (\pm 7 days) while the subject remain on trial. Imaging timing should follow calendar days. On-study scans should be submitted immediately to the imaging .
- p. In subjects who discontinue study therapy without verified disease progression, a radiologic evaluation should be performed at the time of treatment discontinuation (i.e., date of discontinuation \pm 4 week window). If a previous scan was obtained within 4 weeks prior to the date of discontinuation, then a scan at treatment discontinuation is not required.
- q. An optional newly-obtained core or excisional biopsy (FNA not adequate) is requested at any post-treatment time point during the study, (preference would be as close to dosing at Week 12 as possible). A biopsy is also requested at the time of discontinuation for PD, but will not be required. Endoscopic biopsies are permitted.

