8.2.1.2 Dose Modification

Adverse events (both non-serious and serious) associated with pembrolizumab exposure may represent an immunologic etiology. These adverse events may occur shortly after the first dose or several months after the last dose of treatment. Pembrolizumab must be withheld for drug-related toxicities and severe or life-threatening AEs as per Table 3 below. Events of Clinical Interest Guidance Document for supportive care guidelines, including use of corticosteroids.

Table 3

Dose Modification Guidelines for Drug-Related Adverse Events

Toxicity	Hold Treatment For Grade	Timing for Restarting Treatment	Discontinue Subject
Diarrhea/Colitis	2-3	Toxicity resolves to Grade 0-1.	Toxicity does not resolve within 12 weeks of last dose or inability to reduce corticosteroid to 10 mg or less of prednisone or equivalent per day within 12 weeks.
	4	Permanently discontinue	Permanently discontinue
AST, ALT, or Increased Bilirubin	2	Toxicity resolves to Grade 0-1	Toxicity does not resolve within 12 weeks of last dose.
	3-4	Permanently discontinue (see exception below) ¹	Permanently discontinue
Type 1 diabetes mellitus (if new onset) or Hyperglycemia	T1DM or 3-4	Hold pembrolizumab for new onset Type 1 diabetes mellitus or Grade 3-4 hyperglycemia associated with evidence of beta cell failure.	Resume pembrolizumab when patients are clinically and metabolically stable.
Hypophysitis	2-3	Toxicity resolves to Grade 0-1	Toxicity does not resolve within 12 weeks of last dose or inability to reduce corticosteroid to 10 mg or less of prednisone or equivalent per day within 12 weeks.
	4	Permanently discontinue	Permanently discontinue
Hyperthyroidism	3	Toxicity resolves to Grade 0-1	Toxicity does not resolve within 12 weeks of last dose or inability to reduce corticosteroid to 10 mg or less of prednisone or equivalent per day within 12 weeks.
	4	Permanently discontinue	Permanently discontinue

Toxicity	Hold Treatment For Grade	Timing for Restarting Treatment	Discontinue Subject
Hypothyroidism	2-4	Therapy with pembrolizumab can be continued while treatment for the thyroid disorder is instituted	Therapy with pembrolizumab can be continued while treatment for the thyroid disorder is instituted.
Infusion Reaction	3-4	Permanently discontinue	Permanently discontinue
Pneumonitis	2	Toxicity resolves to Grade 0-1	Toxicity does not resolve within 12 weeks of last dose or inability to reduce corticosteroid to 10 mg or less of prednisone or equivalent per day within 12 weeks.

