 - Treat with an initial dose of IV corticosteroid followed by oral corticosteroids. When symptoms improve to Grade 1 or less, steroid taper should be started and continued over no less than 4 weeks. Replacement of appropriate hormones may be required as the steroid dose is tapered.
- **Hepatic:**
 - For **Grade 2** events, monitor liver function tests more frequently until returned to baseline values (consider weekly).
 - Treat with IV or oral corticosteroids
 - For **Grade 3-4** events, treat with intravenous corticosteroids for 24 to 48 hours.
 - When symptoms improve to Grade 1 or less, a steroid taper should be started and continued over no less than 4 weeks.
- **Renal Failure or Nephritis:**
 - For **Grade 2** events, treat with corticosteroids.
 - For **Grade 3-4** events, treat with systemic corticosteroids.
 - When symptoms improve to Grade 1 or less, steroid taper should be started and continued over no less than 4 weeks.
- **Management of Infusion Reactions:** Signs and symptoms usually develop during or shortly after drug infusion and generally resolve completely within 24 hours of completion of infusion.

Table 4 below shows treatment guidelines for subjects who experience an infusion reaction associated with administration of pembrolizumab (MK-3475).

Table 4 Infusion Reaction Treatment Guidelines

NCI CTCAE Grade	Treatment	Premedication at subsequent dosing
Grade 1 Mild reaction; infusion interruption	Increase monitoring of vital signs as medically indicated until the subject is deemed medically	None

NCI CTCAE Grade	Treatment	Premedication at subsequent dosing
not indicated; intervention not indicated	stable in the opinion of the investigator.	

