10.0 TRIAL PROCEDURES

10.1 Trial Procedures

The Trial Flow Chart summarizes the trial procedures to be performed at each visit. Individual trial procedures are described in detail below. It may be necessary to perform these procedures at unscheduled time points if deemed clinically necessary by the investigator.

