10.1.3 Laboratory Procedures/Assessments

Details regarding specific laboratory procedures/assessments to be performed in this trial are provided belowLaboratory Safety Evaluations (Hematology, Chemistry and Urinalysis)

Laboratory tests for hematology, chemistry, urinalysis, and others are specified in Table 5.

Table 5 Laboratory Tests

Hematology	Chemistry	Urinalysis	Other
Hematocrit	Albumin	Blood	Serum β -human chorionic gonadotropin†
Hemoglobin	Alkaline phosphatase	Glucose	(β -hCG)†
Platelet count	Alanine aminotransferase (ALT)	Protein	PT (INR)
WBC (total and differential)	Aspartate aminotransferase (AST)	Specific gravity	aPTT
Red Blood Cell Count	Lactate dehydrogenase (LDH)	Microscopic exam (If abnormal)	Total triiodothyronine (T3)
Absolute Neutrophil Count	Uric Acid	results are noted	Free tyroxine (T4)
Absolute Lymphocyte Count	Calcium	Urine pregnancy test †	Thyroid stimulating hormone (TSH)
	Chloride		
	Glucose		Blood for correlative studies
	Phosphorus		
	Potassium		
	Sodium		
	Magnesium		
	Total Bilirubin		
	Direct Bilirubin (If total bilirubin is elevated above the upper limit of normal)		
	Total protein		
	Blood Urea Nitrogen		

† Perform on women of childbearing potential only. If urine pregnancy results cannot be confirmed as negative, a serum pregnancy test will be required.

Laboratory tests for screening or entry into the Second Course Phase should be performed within 10 days prior to the first dose of treatment. After Cycle 1, pre-dose laboratory procedures can be conducted up to 72 hours prior to dosing. Results must be reviewed by the investigator or qualified designee and found to be acceptable prior to each dose of trial treatment.

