10.2.3.2 Events of Clinical Interest

Selected non-serious and serious adverse events are also known as Events of Clinical Interest (ECI) and must be recorded as such on the Adverse Event case report forms/worksheets and reported within 24 hours to IRB and within 2 working days to Merck Global Safety. (Attn: Worldwide Product Safety; [contact])Events of clinical interest for this trial include:

1. an overdose of Merck product, as defined in Section 10.2.1 - Definition of an Overdose for This Protocol and Reporting of Overdose to Merck, that is not associated with clinical symptoms or abnormal laboratory results.
2. an elevated AST or ALT lab value that is greater than or equal to 3X the upper limit of normal and an elevated total bilirubin lab value that is greater than or equal to 2X the upper limit of normal and, at the same time, an alkaline phosphatase lab value that is less than 2X the upper limit of normal, as determined by way of protocol-specified laboratory testing or unscheduled laboratory testing.*

***Note:** These criteria are based upon available regulatory guidance documents. The purpose of the criteria is to specify a threshold of abnormal hepatic tests that may require an additional evaluation for an underlying etiology.

1. Additional adverse events:

ECIs (both non-serious and serious adverse events) identified in this guidance document from the date of first dose through 90 days following cessation of treatment, or 30 days after the initiation of a new anticancer therapy, whichever is earlier, need to be reported within 24 hours to IRB and within 2 working days to Merck Global Safety. (Attn: Worldwide Product Safety; [contact]), regardless of attribution to study treatment, consistent with standard SAE reporting guidelines.

Subjects should be assessed for possible ECIs prior to each dose. Lab results should be evaluated and subjects should be asked for signs and symptoms suggestive of an immune-related event. Subjects who develop an ECI thought to be immune-related should have additional testing to rule out other etiologic causes. If lab results or symptoms indicate a possible immune-related ECI, then additional testing should be performed to rule out other etiologic causes. If no other cause is found, then it is assumed to be immune-related.

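### Flow chart note l halves CBC and chemistry testing after Cycle 6, although section 10.1.3 requires acceptable results before each dose

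*Combined protocol and SAP*

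**What the plan says.** The flow chart in section 9.1 marks CBC and chemistry at screening, at each of Cycles 2 to 6, at discontinuation and at the safety follow-up. Note l is attached to both rows and again to their Cycle 6 cells. It places screening tests within 10 days of the first dose, allows later samples to be taken up to 72 hours early, and then says "To be repeated every 2 cycles after Cycle 6". It gives CEA and CA 19-9 a schedule of their own.

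Section 10.1.3 repeats the 72-hour window for pre-dose laboratory work. Its next sentence reads "Results must be reviewed by the investigator or qualified designee and found to be acceptable prior to each dose of trial treatment".

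Table 3 (section 8.2.1.2) makes dosing depend on these results. In the row "AST, ALT, or Increased Bilirubin", Grade 2 means hold, and Grade 3-4 means permanent discontinuation, with a separate rule for subjects with liver metastases who start at Grade 2.

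Two other texts give context. The header over the Cycle 5 and 6 columns reads "To be repeated beyond 6 cycles", and both columns are marked for CBC and chemistry. Section 10.2.3.2 says "Subjects should be assessed for possible ECIs prior to each dose".

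**The concern.** The two instructions give different answers to a practical question: may Cycle 7 be infused without new blood results? Note l schedules none. Section 10.1.3 appears to require them, because a 72-hour window followed by a review before each dose most naturally refers to that dose's own sample.

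At stake is the working of the hepatic rule in Table 3. A rise that causes symptoms is likely to surface at the visit, since adverse event review, examination, vital signs and ECOG status are scheduled every cycle. Known drug-related abnormalities are followed to resolution, and for Grade 2 hepatic events section 8.4.1 tells the investigator to "monitor liver function tests more frequently until returned to baseline values". Those last two safeguards start only once an abnormality has been found. The remaining gap is a new rise without symptoms, present before an odd-numbered dose after Cycle 6. Under note l that dose could be given although Table 3 would withhold it.

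**Working it through.** **Inputs.** Dosing every 21 days (8.2.2); 35 administrations or 24 months, whichever is later (8.6); dosing window of 3 days either side (8.2.2); samples up to 72 hours early (note l, 10.1.3); about 24 months from first consent to last visit and 12 months of enrollment (1.0); screening of up to 28 days (1.0); safety visit about 30 days after the last dose (10.1.5.4.1).

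**The plan's own figure.** With 24 months taken as 730 days, doses fall on days 0, 21, ..., 714. The count is floor(730/21) + 1 = 34 + 1 = 35, which matches section 8.6.

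**Coverage over 35 doses under note l.**
- Cycle 1 is covered by screening and Cycles 2 to 6 by the grid: 6 doses.
- Cycles 8, 10, ..., 34: (34 − 8)/2 + 1 = 14 doses.
- Covered: 6 + 14 = 20. Not covered: Cycles 7, 9, ..., 35 = (35 − 7)/2 + 1 = 15, and 15/35 = 43%.
- Sensitivity: 14 of 35 if the two-cycle sequence is read as starting at Cycle 7; 16 of 35 if screening labs are not counted for Cycle 1.
- With a draw before every dose: 0 of 35.

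**Coverage within the estimated timeline.** Assumptions: no dose delays, and last dose 30 days before trial end, that is by day 700.
- First subject, with 0 to 28 days of screening: 700 to 672 days available, so floor(700/21) + 1 = 34 or 672/21 + 1 = 33 doses. Not covered: Cycles 7, ..., 33 = 14, or 41% to 42%.
- Subject starting at day 365: 335 days available, so floor(335/21) + 1 = 16 doses. Not covered: Cycles 7, 9, 11, 13, 15 = 5, or 31%.
- Subject stopping by Cycle 6: 0.

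Thirty-five doses plus the safety visit need 714 + 30 = 744 days, more than 730. The 15-of-35 figure therefore falls just outside the estimated timeline.

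**Age of the latest scheduled result at an uncovered dose.** It is 21 days if the sample was taken on Day 1 of the previous cycle, and 21 + 3 = 24 if it was taken 72 hours early. With the dosing window on both doses, the range is 21 − 6 = 15 to 21 + 6 + 3 = 30 days. The nominal gap between scheduled liver tests goes from 21 to 42 days.

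**The case against.** The best defence is that note l is deliberate and that the chart governs. Section 8.2.2 ties each infusion to completion of the chart's procedures, and section 10.1.5 refers to the chart for visit requirements. Imaging, CEA and CA 19-9 also become less frequent after about six months. Section 10.1.3 sets no draw frequency in so many words, so it could mean review of whatever result is latest. This reading is possible, but it sits poorly with the 72-hour pre-dose window in the sentence just before. If it was intended, section 10.1.3 needs rewording, so the contradiction remains either way. Section 10.1 says "The Trial Flow Chart summarizes the trial procedures to be performed at each visit" and refers to the text for detail, but no rule of precedence is stated.

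Three stronger readings are tempting, and the documents do not support them:
- *The repeated Cycle 5-6 columns are a second conflict.* Note l is printed on the Cycle 6 cells and can be a specific exception to a general header.
- *The ECI text is a third conflict.* One listed ECI is defined only by laboratory values, beginning with "an elevated AST or ALT lab value that is greater than or equal to 3X the upper limit of normal", but the same item limits itself to tests the protocol schedules or unscheduled tests. It creates no test before every dose.
- *Fifteen of 35 is the usual exposure, or a ceiling.* It assumes a full course, which the estimated timeline does not quite hold. It is not a maximum either, because section 8.6 takes the later of two limits and retreatment is allowed.

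Nor should a reader expect practice to differ between sites: the trial is single-center, and one investigator can settle the reading once.

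**Conclusion.** The conflict between note l and section 10.1.3 holds and is in current text. Following note l leaves alternate doses after Cycle 6 without scheduled CBC or chemistry: 5 of 16 to 14 of 33 or 34 for a subject treated without interruption within the estimated timeline, 15 of 35 for a completed course, and none for early stoppers. The consequence is a possible delay of one cycle, and one dose given, before a silent hepatic abnormality is seen. How often that would happen cannot be estimated, since the documents give neither a rate of such events nor a distribution of treatment duration. This is a minor safety-monitoring inconsistency. A reader might infer that it weakens the efficacy result, but the ORR analysis and the sample size do not depend on it.

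**What to change.** Amend note l so that CBC and chemistry are drawn within 72 hours before every dose throughout treatment. Limit the every-2-cycles rule after Cycle 6 to T3, FT4 and TSH, which the grid already marks at Cycles 2, 4 and 6. Leave CEA and CA 19-9 on their stated schedule.

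The change is one sentence. The cost is roughly 5 to 15 extra routine draws per long-treated subject, at visits already attended for examination and infusion. The alternative, restricting section 10.1.3 to results due under the chart, would also remove the contradiction but would keep dosing on results about three weeks old.
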